## **1. Study Rationale and Objectives**

This prospective observational study aims to evaluate and compare the predictive accuracy of perioperative risk scoring systems in patients undergoing gastrointestinal malignancy surgery. The primary objective is to assess the sensitivity of ASA, SAS, Portsmouth-POSSUM, ACS-NSQIP, and ARISCAT scores in predicting postoperative mortality. Secondary objectives include evaluating the ability of these scores to predict postoperative pulmonary and extrapulmonary complications, ICU admission, and length of hospital and ICU stay.

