## **4. Outcome Measures**

Primary outcome: postoperative mortality (30-day and 60-day). Secondary outcomes: postoperative pulmonary and extrapulmonary complications, ICU admission, length of hospital stay, and ICU stay.

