## **5. Data Collection**

Preoperative, intraoperative, and postoperative data will be collected prospectively. Mortality data will be assessed at 30 and 60 days using hospital records and telephone follow-up.

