## **6. Statistical Analysis Plan**

Statistical analyses will be performed using SPSS version 22.0. Continuous variables will be presented as mean  $\pm$  standard deviation or median (interquartile range). Categorical variables will be presented as frequencies and percentages. Receiver operating characteristic (ROC) curve analysis will be used to assess the predictive performance of each scoring system. Sensitivity, specificity, and area under the curve (AUC) values will be calculated. A p-value  $< 0.05$  will be considered statistically significant.

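### The scores are to predict length of hospital stay and ICU stay, but the only method named for prediction is ROC analysis, which needs a yes/no outcome, and the plan gives no cut-off in days.

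*Combined protocol and SAP*

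**What the plan says.** Section 1 states that the study "aims to evaluate and compare the predictive accuracy of perioperative risk scoring systems". Its secondary objectives end with "ICU admission, and length of hospital and ICU stay". Section 4 repeats the list: "Secondary outcomes: postoperative pulmonary and extrapulmonary complications, ICU admission, length of hospital stay, and ICU stay". Neither section gives a number of days that would make a stay prolonged.

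On prediction, section 6 says "Receiver operating characteristic (ROC) curve analysis will be used to assess the predictive performance of each scoring system" and "Sensitivity, specificity, and area under the curve (AUC) values will be calculated". Its only provision for continuous variables is descriptive; the sentence begins "Continuous variables will be presented as mean" and offers a median with interquartile range as the alternative. The section otherwise names the software, the summary for categorical variables and a 0.05 significance threshold.

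Sections 1 to 6 contain no correlation, regression, time-to-discharge model or concordance index. Section 6 does not say that ROC is the exclusive method.

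**The concern.** Sensitivity and specificity require each patient to be a case or a non-case. Mortality by a fixed day, a complication and ICU admission all meet that requirement. A number of days in hospital or in ICU does not until someone chooses a threshold.

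The missing threshold has three consequences:

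- **Lost information.** A split treats all stays on the same side of the cut as equal. This makes it harder to detect that a score predicts stay, and harder to tell two scores apart, which is the stated aim.
- **Freedom of choice.** With no cut fixed in advance, one could be picked after looking at the results, and the nominal 0.05 would then no longer hold.
- **A moving target.** The AUC itself depends on where the cut is placed, so a reported value cannot be interpreted or compared until the cut is known.

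**Working it through.** **Text check.** The stays are listed as outcomes to be predicted (sections 1 and 4). The method named for prediction needs two classes (section 6). No section supplies a cut-off or another method. The plan states no power, sample size or event count, so there is no figure of its own to reproduce.

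**Inputs for the illustration.** From the documents: significance level 0.05, taken as two-sided because the plan does not say. Assumed: n = 300; hospital stay log-normal, rounded to whole days, median 9, log-SD 0.5; latent score-stay correlation ρ of 0, 0.20 or 0.40.

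**Hand check at ρ = 0.20** (ignoring rounding to days):

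- Spearman: r_s = (6/π)·arcsin(ρ/2) = 1.910 × 0.1002 = 0.191. Then z = 0.191 × √299 = 3.31, and power = Φ(3.31 − 1.96) = Φ(1.35) = 91%.
- ROC, median split: AUC = 0.5 + (2/π)·arcsin(ρ/√2) = 0.5 + 0.637 × 0.1419 = 0.590. The standard error with no association is √[(n+1)/(12·n₁·n₀)] = √[301/(12 × 150 × 150)] = 0.0334. Then z = 0.0903/0.0334 = 2.71, and power = Φ(0.75) = 77%.

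**Simulation, one score against no association, n = 300:**

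| ρ | Spearman | ROC, median split | ROC, 75th percentile | ROC, 90th percentile |
|---|---|---|---|---|
| 0.20 | 91% | about 77% | about 68% | about 48% |
| 0.40 | 100% | 100% | 100% | 98% |

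At 0.20 the loss is 91 − 77 = 14, 91 − 68 = 23 and 91 − 48 = 43 percentage points. At 0.40 it is at most 2.

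**Simulation, two scores compared in the same patients.** Assumed: n = 300, score-stay correlations 0.40 and 0.20, correlation 0.5 between the scores. A test of dependent Spearman correlations has about 94% power. A paired DeLong test has about 79%, 70% and 50% at the same three splits. The loss for comparing scores therefore persists even when one of them is strongly related to stay.

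**False positives with no association, n = 300:**

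- One fixed cut: about 5%.
- Best of the three cuts: 12–13%. If the cuts were independent it would be 1 − 0.95³ = 14.3%; they overlap, so slightly less is expected.
- All whole-day cuts leaving 10–90% of patients above: about 27%.
- All whole-day cuts leaving 2–98% above: about 38–42% across simulation runs.

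The last two figures depend on the search limits and the assumed spread of stay. Neither is an upper bound.

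**Dependence of the AUC on the cut.** Moving the cut from the median to the 90th percentile changes the AUC from 0.636 to 0.663 at ρ = 0.3, and from 0.731 to 0.772 at ρ = 0.5.

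**The case against.** The strongest reply is that unspecified is not mis-specified. Section 6 is one short paragraph. It does not say that ROC will be applied to the stays, and it does not exclude other methods. The method for the stays may simply not have been written down, in which case the power and false-positive figures describe an analysis nobody intends. This stands as a limit on the figures. It does not remove the point: on that reading two listed outcomes have no prespecified predictive analysis, and on the other they have one that cannot be run without an unstated choice.

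A second reply is that a prolonged-stay outcome is legitimate. That is also right. If the number of days is fixed beforehand, the test keeps its 5% error rate, and one sentence giving that number would close the gap. Leaving the days unsplit is the more efficient choice, not the only valid one.

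A third is that every input to the power figures is assumed, and that for a single score with correlation 0.40 the loss nearly vanishes. This is correct. The figures show what could be lost, not what will be.

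A reader might infer that the cut will be chosen after the data are seen. No section says or implies this; the plan only leaves it possible. A reader might also infer that in-hospital deaths, by shortening stays, bias these analyses. The documents give no timing of deaths in relation to discharge; section 5 says only "Mortality data will be assessed at 30 and 60 days using hospital records and telephone follow-up". No bias is shown, and the handling of deaths is a matter for clarification.

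**Conclusion.** The point holds for length of hospital stay and ICU stay only. The plan makes both outcomes to be predicted, names for prediction only a method that needs two classes, and supplies neither a cut-off nor an alternative. ICU admission appears in the same list but is binary and unaffected, as are mortality and complications. The primary objective is not touched.

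The size is illustrative. It rests on assumed sample size, stay distribution and correlations, and on the reading that ROC would be applied to the stays. On those terms the cost ranges from almost nothing (one strong score, 300 patients) to more than 40 points of power (a weak score, or two scores compared, with a 90th percentile split). A cut chosen afterwards would raise the false-positive rate to about 13% with three candidates, and higher with more. The documents do not support the stronger claim that the planned analysis is invalid. The change should be made because it is cheap and closes a real gap.

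**What to change.** Amend section 6 as follows:

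- Keep ROC analysis for mortality, complications and ICU admission.
- Analyse hospital stay and ICU stay undichotomised. Report a concordance index or Spearman correlation with a 95% CI for each score, and compare scores by the paired difference in the same patients.
- If a prolonged-stay ROC analysis is also wanted, state the number of days before the data are seen.

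Two clarifications belong alongside this. First, state how in-hospital deaths count in each stay, with a discharged-alive sensitivity analysis for hospital stay; ranking deaths as the worst outcome would overlap with the mortality outcome. Second, state whether ICU stay is analysed among admitted patients only or with zeros for the rest.

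The cost is a few sentences, with no new data. There are downsides. The result is a rank measure rather than a number of days. For ICU stay neither option is ideal. With zeros, the analysis nearly repeats ICU admission: the correlation between the two is 0.99 if 20% are admitted. Restricting to admitted patients uses a small subgroup formed after surgery: 0.20 × 300 = 60 patients under the same assumption, with about 29% power at correlation 0.20 and 84% at 0.40.

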## **2. Study Design**

This is a single-center, prospective observational study conducted at a tertiary referral hospital. No additional interventions beyond routine clinical care will be performed.

## **3. Study Population**

Adult patients aged 18 years or older undergoing elective gastrointestinal malignancy surgery under general anesthesia who provide written informed consent will be included.

## **4. Outcome Measures**

Primary outcome: postoperative mortality (30-day and 60-day). Secondary outcomes: postoperative pulmonary and extrapulmonary complications, ICU admission, length of hospital stay, and ICU stay.

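### The plan sets out to compare five risk scores but analyses each one separately, with no paired comparison and no rule for where sensitivity is read

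*Combined protocol and SAP*

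**What the plan says.** All references are to the combined protocol and SAP.

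- **Section 1 (Study Rationale and Objectives), general aim:** to "evaluate and compare the predictive accuracy of perioperative risk scoring systems".
- **Section 1, primary objective:** "The primary objective is to assess the sensitivity of ASA, SAS, Portsmouth-POSSUM, ACS-NSQIP, and ARISCAT scores in predicting postoperative mortality". This covers five scores, and the measure is sensitivity.
- **Section 4 (Outcome Measures):** "Primary outcome: postoperative mortality (30-day and 60-day". Neither time point is ranked above the other. Section 5 (Data Collection) also treats them alike: "Mortality data will be assessed at 30 and 60 days using hospital records and telephone follow-up".
- **Section 6 (Statistical Analysis Plan):** "Receiver operating characteristic (ROC) curve analysis will be used to assess the predictive performance of each scoring system", followed by "Sensitivity, specificity, and area under the curve (AUC) values will be calculated". One threshold, p below 0.05, "will be considered statistically significant"; the hypothesis it applies to is not stated.

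Section 6 names no contrast between scores, no paired method, no cut-off or reference specificity, no confidence interval and no multiplicity rule.

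**The concern.** The aim is comparative, but the analysis is carried out one score at a time. All five scores are measured in the same patients, so a comparison needs the difference between scores and the precision of that difference. Separate per-score results supply neither. If one score reaches p<0.05 and another does not, the first has not been shown to be better.

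The primary measure adds a second difficulty. Sensitivity is not a fixed property of a score, because it rises as the cut-off is loosened and specificity falls. Without a rule fixed in advance, the cut-offs could be chosen after the data are seen, and a difference in sensitivity could reflect only a difference in cut-off.

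What is at stake is any conclusion that one score predicts death better than another. As written, such a conclusion would have no pre-specified basis. The unranked time points add a little to this. Every death by day 30 is also a death by day 60, so agreement between the two is not independent confirmation.

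**Working it through.** The documents give no sample size, death count, power or error rate, so there is no plan figure to reproduce. The only statistical number is the 0.05 threshold. Values marked *assumed* are not from the documents.

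**1. Aim against method.** Section 1 promises a comparison of five scores. Section 6 supplies five separate ROC analyses. Five scores form 5 × 4 / 2 = 10 pairs, and Section 6 gives a method for none of them.

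**2. Why separate results are not enough.** For two scores in the same patients,

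Var(AUC₁ − AUC₂) = Var(AUC₁) + Var(AUC₂) − 2 Cov(AUC₁, AUC₂).

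Per-score output does not contain the covariance. With equal standard errors s and correlation r, the standard error of the difference is s√(2(1 − r)). For *assumed* r of 0.3 and 0.7 this is s√1.4 = 1.18s and s√0.6 = 0.77s. Reading across separate p-values or intervals ignores this.

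**3. Sensitivity without a common specificity.** *Assumed:* binormal scores with equal variance, both with AUC 0.75.

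- AUC = Φ(d/√2), so d = √2 × 0.6745 = 0.954.
- Sensitivity = Φ(d − z), where z is the normal quantile of the specificity.
- Specificity 80%: z = 0.842, so sensitivity = Φ(0.112) = 0.545, or 54% (0.5447 before rounding).
- Specificity 60%: z = 0.253, so sensitivity = Φ(0.701) = 0.758, or 76%.

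Two scores with identical discrimination therefore differ by about 21 points in sensitivity (75.8 − 54.5) through the cut-off alone.

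**4. Would a paired test of sensitivity alone cure this?** No. Take the two equal scores of step 3, with *assumed* correlation 0.3 to 0.7, and apply exact McNemar among the deaths. The chance of a significant result favouring the looser cut-off is:

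| Deaths (*assumed*) | p<0.05 | p<0.005 |
|---|---|---|
| 24 | 26–34% | 5–6% |
| 36 | 44–60% | 14–23% |

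The false preference grows with more deaths, and a stricter threshold does not remove it. A sound comparison of sensitivity has to hold specificity fixed or judge both together.

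**5. Secondary: multiplicity, if pairwise tests were run.** This is conditional on a test that Section 6 does not name. *Assumed:* large samples, five equally good scores with exchangeable normal statistics, and each pair tested at two-sided 0.05.

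- At one time point, at least one of the 10 contrasts is significant when the range of five standard normals exceeds 1.96 × √2 = 2.77. That probability is 0.286, about 29%. A common inter-score correlation cancels out of it.
- Over both time points there are 20 contrasts. The correlation between the 30- and 60-day statistics is taken as √(share of 60-day deaths that occur by day 30), with the share *assumed* to be 50% to 90%. The chance is then 42% falling to 35%.
- For one score tested at both time points it is only 6.5% to 8.3%. This is why the unranked time points are the smaller part.

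**The case against.** The strongest reply is that this is a descriptive, single-centre observational study. The primary objective asks for the sensitivity of the scores to be assessed; the comparative word appears only in the general aim. Section 6 does calculate sensitivity. Such a study may properly report several estimates at two time points without one confirmatory test, and no multiplicity adjustment is then called for.

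Much of this stands. Having two time points and no multiplicity rule is not a defect on every reading. Nor does any section say that the study will end by ranking the scores; that is an inference from the aim.

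It does not dispose of the main point. Section 1 does state a comparative aim, and a descriptive comparison still needs the paired difference and its interval. A descriptive sensitivity also needs a stated cut-off or specificity.

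A reader might infer from the 29% and 35–42% figures that the plan itself carries that false-positive rate. The documents do not support this. Section 6 contains no pairwise test and does not say what p<0.05 applies to. The figures describe what would happen if unadjusted pairwise tests were added.

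**Conclusion.** The concern holds as a gap between aim and method: a comparative aim with no paired comparison, and a primary measure with no rule for where it is read. This follows from Sections 1 and 6 side by side and needs no simulation. It should be put right before analysis.

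The 54% against 76% illustration rests on an assumed AUC of 0.75 and a binormal model. It shows that cut-off choice alone can produce a large apparent difference; it does not predict this study's results. The multiplicity figures are secondary and conditional on an inferred test. The unranked time points are a minor part.

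Two stronger readings are tempting and not supported. One is that two primary time points without adjustment are an error in themselves; that depends on whether significance claims are intended, which the plan does not say. The other is that the study has too few deaths to separate the scores; with no sample size or death count in the documents, this cannot be judged.

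**What to change.** **Main change.** In Section 6, replace reliance on separate per-score results with wording such as:

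> Scores are compared by paired differences in AUC for mortality at [one time point chosen by the sponsor before analysis; the other supportive], using DeLong's method, each with a 95% confidence interval as the main presentation.

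Amend Section 1 so that its primary measure agrees.

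**If sensitivity stays primary.** Either compare the scores by paired differences in sensitivity, with 95% confidence intervals, at a common pre-specified specificity; or report paired differences in sensitivity and specificity jointly and claim superiority only if specificity is not worse. Do not test sensitivity alone at separate cut-offs.

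**Significance claims.** State whether any are intended between scores. If so, apply Holm over the contrasts; the first step for 10 pairs is 0.05/10 = 0.005. If not, say that the comparison is by estimates and confidence intervals; no adjustment is then needed.

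**Cost.** No new data are needed, since Section 5 already collects mortality at both time points. The change is a paragraph in Section 6 and an aligned sentence in Section 1. Conclusions will be more cautious, and choosing 30 days would mean no more events than 60 days and probably fewer. DeLong's method is approximate with few deaths, and no option here cures the imprecision that few deaths bring. Section 6 says "Statistical analyses will be performed using SPSS version 22.0"; whether that version runs the paired contrast was not verified, and other software must be named if it does not.

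### ICU admission and ICU stay are not split into planned and unplanned, so if some ICU beds are arranged in advance because of perceived risk, the comparison of scores on these secondary outcomes can be distorted

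*Combined protocol and SAP*

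**What the plan says.** Section 4 of the combined protocol and SAP gives the secondary outcomes in one line: "postoperative pulmonary and extrapulmonary complications, ICU admission, length of hospital stay, and ICU stay". Section 1 makes them prediction targets, with the aim of "evaluating the ability of these scores to predict postoperative pulmonary and extrapulmonary complications, ICU admission, and length of hospital and ICU stay". ICU admission has no further definition, and no distinction is drawn between an admission arranged ahead of time and one prompted by events.

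Three other parts of the plan bear on this:

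- Section 3 restricts the cohort to patients having "elective gastrointestinal malignancy surgery under general anesthesia".
- Section 2 says of care: "No additional interventions beyond routine clinical care will be performed". The plan does not say whether the clinicians who decide on ICU know the scores.
- Section 6 names ROC analysis, with AUC, sensitivity and specificity, as the way to judge each score. It does not exclude pre-arranged ICU admissions or analyse them separately. Section 5 describes prospective data collection but names no item for when or why ICU was decided.

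**The concern.** In elective surgery an ICU bed can be arranged before the operation. Such an admission reflects someone's view of the patient's risk. It is a different kind of event from an admission that nobody arranged and that a new problem made necessary. If both occur and are pooled, each score is tested partly on agreement with the local booking decision and partly on prediction of unplanned need.

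The scores need not be affected equally. One that resembles the clinicians' own risk judgement would be favoured (ASA is the obvious candidate, though the documents do not say so). One that captures something else would be penalised. The study exists to compare scores, so a shift that differs between them matters more than a general shift in AUC. ICU stay is exposed in the same way, because an arranged stay adds ICU time whether or not the patient deteriorates.

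**Working it through.** **Inputs.** The plan gives no ICU admission rate, booking rate, expected AUC or sample size for this outcome, so there is no figure to reproduce. From the documents come the unqualified outcome (sections 1 and 4), the elective cohort (section 3), routine care (section 2) and the ROC method (section 6). Every number below is an assumption chosen to show direction and range.

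**Step 1: one score, exact identity.** Take never-admitted patients as controls. Let w be the planned share of ICU admissions. Then

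AUC(any ICU) = w × AUC(planned) + (1 − w) × AUC(unplanned).

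With AUC(unplanned) = 0.65:

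| AUC(planned) | w = 25% | w = 50% | w = 75% |
|---|---|---|---|
| 0.90 | 0.225 + 0.4875 = 0.71 | 0.45 + 0.325 = 0.78 | 0.675 + 0.1625 = 0.84 |
| 0.80 | 0.20 + 0.4875 = 0.69 | 0.40 + 0.325 = 0.73 | 0.60 + 0.1625 = 0.76 |
| 0.65 | 0.65 | 0.65 | 0.65 |
| 0.50 | 0.125 + 0.4875 = 0.61 | 0.25 + 0.325 = 0.58 | 0.375 + 0.1625 = 0.54 |

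At w = 0 the result is 0.65 in every row. The pooled AUC can therefore rise, stay the same or fall, depending on how closely booking follows the score.

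**Step 2: two equally able scores, simulation of 1,000,000 patients.**

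- The scores X1 and X2 are standard normal with correlation 0.5.
- Unplanned need is a normal variable correlated 0.28 with each score. The top 10% of patients have an unplanned need, which gives an AUC of about 0.65 for each score.
- Booking is a normal variable B = c × X1 + √(1 − c²) × noise, and the top p of patients are booked. Its correlation with X2 is then 0.5 × c.
- The pooled outcome is booked or unplanned.

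With p = 10% booked (results good to about 0.01):

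| c (booking with X1) | 0.5c (booking with X2) | AUC X1 | AUC X2 |
|---|---|---|---|
| 0.8 | 0.40 | 0.80 | 0.69 |
| 0.6 | 0.30 | 0.75 | 0.67 |
| 0.4 | 0.20 | 0.69 to 0.70 | 0.64 |
| 0.28 | 0.14 | 0.66 | 0.62 |
| 0 | 0 | 0.58 | 0.58 |

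The true values are equal, at about 0.65. In this model a score gains roughly when its correlation with booking exceeds its correlation with unplanned need (0.28), and loses when it falls short. At c = 0.28 X1 is not materially inflated, yet the two scores still separate because X2 drops. At c = 0 both look worse and the ranking is undisturbed.

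Fewer bookings shrink the effect. At c = 0.8 the AUCs are about 0.75 vs 0.69 with 5% booked, 0.70 vs 0.67 with 2%, and 0.68 vs 0.66 with 1%. With none booked there is no distortion.

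**Step 3: does separating the types help?** For unplanned admission among patients not booked, the AUCs at c = 0.8 return to about 0.64 vs 0.65, so near-equality is restored.

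These calculations cover ICU admission only. The effect on ICU stay was not quantified.

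**The case against.** The strongest reply is that the plan never mentions ICU booking. That surgery is elective and care routine makes advance booking possible but does not show that it happens at this hospital. The outcome is undefined; the plan does not state that booked admissions count. This stands, and it is why the point is conditional.

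A reader might go further and infer that the scores will look falsely accurate, or that the outcome is circular in the sense of incorporation bias. The documents support neither. Incorporation bias needs a score to form part of the reference outcome, and nothing in the plan says that any of the five scores determines ICU admission. Nor is the direction fixed: the working shows gain, no change and loss according to how closely booking follows the score.

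A second reply is that all ICU admissions are a legitimate target. Section 1 lists them beside length of stay, which can be read as an interest in resource use. The plan nowhere says that unexpected deterioration is what the scores should predict. This also stands, and it argues against making unplanned admission the only ROC outcome.

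Third, restricting the analysis to patients not booked removes those whom clinicians judged to be at higher risk, so it answers a question about a different population. That is a reason to show both results. None of these replies supplies a way to tell, from the data as now planned, how far a difference between scores reflects booking.

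**Conclusion.** The point holds in conditional form. Without a planned/unplanned split, the analysis of ICU admission can separate scores that are equally good at predicting unplanned need, and ICU stay is open to the same mixing. Under the stated assumptions, two scores with AUC about 0.65 can appear as far apart as 0.80 vs 0.69 with 10% booked and a booking correlation of 0.8. The gap narrows as booking becomes rarer or less tied to one score, and there is no distortion when no admission is planned. Neither the booking rate nor the correlation can be taken from the documents, so these figures show what could happen and do not estimate what will.

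Only secondary outcomes are affected. The primary outcome, mortality at 30 and 60 days, does not depend on how ICU admission is defined.

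**What to change.** - **Sections 4 and 5:** record prospectively, for each ICU admission, whether it was planned before surgery or unplanned, and when and why it was decided. The time and reason matter for decisions at the end of surgery, so that one prompted by an intraoperative event is not classed as precautionary. State also whether those deciding on ICU have access to the scores.
- **Section 6:** report ROC results for unplanned admission among patients with no planned admission, alongside those for all admissions. Report ICU stay separately by type of admission.

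The cost is one extra item on the form, with its time and reason, and a sentence in each section. The unplanned analysis will have fewer events and wider intervals, and it leaves out booked, typically higher-risk, patients, so both sets of results should be shown. Because data are collected prospectively, recording the decision as it is made is cheap; reconstructing its timing later would be less reliable. If planned admissions prove rare, the record will show it and little is lost.
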